- External monitoring is performed by an independent Clinical Research Associate (CRA), which provides regular site monitoring and data validation to ensure data quality and patient safety.
- The Data Safety Monitoring Board (DSMB) periodically reviews accumulated safety data, including adverse event frequencies and severity, to address any unexpected risks promptly.

Substudies

The following substudies are planned:

- Echocardiographic substudy,
- Magnetic Resonance Imaging substudy.

Subgroup analysis

The analysis of the following subgroups is planned in the study:

- Women versus men,
- Patients with prehospital time delay duration 3 hours and longer versus less than 3 hours,
- Patients with and without out-of-hospital cardiac arrest,
- Patients with and without mechanical ventilation,
- Patients with and without mechanical circulatory support (e.g., IMPELLA, ECMO)*
- Patients with and without persistent coma (Glasgow Coma Scale < 8) at admission,
- Patients with and without diabetes,
- Patients with and without obesity,
- Patients who are cigarette smokers versus non-smokers,
- Patients with and without multivessel disease,
- Patients with and without a history of heart failure.

**A time-dependent covariate analysis will be performed instead of standard subgroup analysis to prevent bias due to treatment-dependent selection effects for mechanical circulatory support (MCS), which may occur post-randomization.*

Handling of Post-Randomization Events (MCS)

MCS use will be modeled as time-dependent covariates in survival analyses to avoid bias introduced by post-randomization treatment effects. These covariates will be introduced into the primary and secondary outcome models as follows:

Time-Dependent Covariate Analysis

To accurately account for the influence of MCS on study outcomes, these variables will be modeled as time-dependent covariates within the Cox proportional hazards model:

Primary Model:

- $HR = \beta_1(\text{Treatment}) + \beta_2(\text{Mechanical Ventilation (time-dependent)}) + \beta_3(\text{ECMO (time-dependent)}) + \epsilon$
- This ensures that the estimation of treatment effects is not confounded by patients who deteriorate and need additional support after randomization.

Competing Risks Model (Fine & Gray) for Non-MACE Outcomes:

- If MCS is strongly associated with mortality before the primary endpoint, a competing risks approach will be applied using the Fine & Gray subdistribution hazard model.

Sensitivity Analysis

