- Inverse Probability of Treatment Weighting (IPTW) will be applied as an alternative approach to adjusting for potential differences between patients requiring MCS and those who do not.

Reporting & Interpretation

- The Kaplan-Meier curves for MACE outcomes will be stratified based on whether patients required MCS, but formal statistical comparisons will be limited to time-dependent Cox models to avoid survivor bias.
- Forest plots will be presented for pre-randomization subgroups only.

Analysis population

The patients enrolled in the study will be summarized in a CONSORT flow diagram. The analyses will be conducted using a modified intention-to-treat principle (MITT), an intention-to-treat principle (ITT), and a per-protocol (PP) approach. The MITT population includes all randomized patients in the trial who received a dose of the study drug. The ITT encompasses all trial-randomized patients, and the PP population consists of all randomized patients who received the full dose of the study drug as per protocol. Treatment classification in all scenarios will be based on the randomized treatment. The MITT will serve as the primary analysis approach; analyses based on ITT and PP populations will be considered secondary and confirmatory.

Data Sharing

The data used in the published scientific papers will be available according to the requirements of the respective scientific journals. To mitigate the risk to patient privacy, the data will be

anonymized and identified through masking or generalization of direct and some indirect identifiers. Only variables used in the given analysis will be included in the shared dataset.

Statistical analysis

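### The Cox model that replaces the MCS subgroup analysis has main effects only, so it adjusts for support but cannot show whether the cangrelor effect differs by MCS

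*SAP*

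**What the plan says.** The SAP section *Subgroup analysis* lists, among the planned subgroups, "Patients with and without mechanical circulatory support (e.g., IMPELLA, ECMO". A footnote to that line changes the method: "A time-dependent covariate analysis will be performed instead of standard subgroup analysis to prevent bias due to treatment-dependent selection effects". The reason given is that MCS may begin after randomization.

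Under *Time-Dependent Covariate Analysis* the SAP prints the replacement model: "HR = \beta_1(\text{Treatment}) + \beta_2(\text{Mechanical Ventilation (time-dependent)}) + \beta_3(\text{ECMO (time-dependent)}) + \epsilon". Its purpose is stated directly below: "This ensures that the estimation of treatment effects is not confounded by patients who deteriorate and need additional support after randomization".

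Under *Sensitivity Analysis*, inverse probability weighting is offered "as an alternative approach to adjusting for potential differences between patients requiring MCS and those who do not". Under *Reporting & Interpretation*, Kaplan-Meier curves for MACE are to be stratified by whether MCS was required, but "formal statistical comparisons will be limited to time-dependent Cox models to avoid survivor bias". The same section adds: "Forest plots will be presented for pre-randomization subgroups only".

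*Additional analyses* describes confounder-adjusted logistic regression for subgroups and names no interaction test.

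**The concern.** A with/without subgroup analysis asks whether the treatment effect differs between the two groups. The SAP keeps that question on its list and assigns it to a model that lacks the term needed to answer it. If the cangrelor effect does depend on support, the model returns a single averaged HR that is right for neither group, and it would be reported under a subgroup heading. A reader of the results could take this as evidence of a consistent effect, when consistency was imposed by the model and not tested.

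There is a second gap in the same equation. The subgroup line names IMPELLA and ECMO as MCS, but the model has a term for ECMO only. Its other support term is mechanical ventilation, which is not MCS and has its own line in the subgroup list.

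**Working it through.** **1. What the printed model can estimate.** The equation is read as the linear predictor of the log hazard, since the SAP calls it a Cox model:

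log h(t) = log h0(t) + β1·Trt + β2·MV(t) + β3·ECMO(t)

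Treatment HR without ECMO: exp(β1 + β3·0) / exp(β3·0) = exp(β1).
Treatment HR with ECMO: exp(β1 + β3) / exp(β3) = exp(β1).

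The two are equal by construction. A difference needs a further term β4·Trt×MCS(t); the HR is then exp(β1) off support and exp(β1 + β4) on support. This is algebra and rests on no assumed numbers.

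**2. Whether another section supplies the missing estimate.**
- Kaplan-Meier curves stratified by MCS: descriptive only, and the SAP does not say whether they are also split by arm.
- Inverse probability weighting: an adjustment for differences between MCS and non-MCS patients, not a treatment effect by MCS.
- Logistic models in *Additional analyses*: no interaction named, and the footnote takes MCS out of the standard subgroup route.
- Forest plots: pre-randomization subgroups only.

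None estimates or tests a treatment effect by MCS status.

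**3. Illustration (all parameters assumed).** Simulated start-stop data: 20,000 patients, 1:1, follow-up to day 30, hazard 0.018/day in controls off support, support starting at 0.015/day independently of treatment, support multiplying the hazard by 3. There was no ventilation term. About 30% to 40% of events fell on support.

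| True HR off / on MCS | Main-effects model | With Trt×MCS(t): off / on |
|---|---|---|
| 0.60 / 1.00 | 0.74 | 0.62 / 0.98 |
| 0.50 / 1.25 | 0.74 | 0.51 / 1.24 |
| 1.00 / 0.60 | 0.87 | 1.01 / 0.59 |
| 0.69 / 0.69 | 0.70 | 0.71 / 0.67 |

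The first two rows are clearly different truths, and the main-effects form cannot tell them apart.

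**4. Precision of an added interaction.** The plan's own figure first. *Power analysis for the superiority scenario* gives 50% vs 38%, power 0.8, significance level 0.05 and a total of 536. With pooled variance and a two-sided test (sidedness is not stated), mean rate 0.44:

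n per arm = [1.960·√(2·0.44·0.56) + 0.842·√(0.5·0.5 + 0.38·0.62)]² / 0.12² = 267.4, rounded up to 268; total 536. It reproduces.

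Expected events: 268·0.50 + 268·0.38 = 134 + 101.84 = 235.84, about 236.

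With a share q of events on MCS (not in the SAP, so a range is assumed):

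SE(log ratio of HRs) = √[4/(235.84·q) + 4/(235.84·(1−q))]
Power for a ratio of 0.6 = Φ(|ln 0.6|/SE − 1.96), with |ln 0.6| = 0.511
Ratio detectable with 80% power = exp[−(1.960 + 0.842)·SE]

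| q | SE | Power for ratio 0.6 | Ratio detectable at 80% power |
|---|---|---|---|
| 10% | 0.434 | 22% | 0.30 |
| 20% | 0.326 | 35% | 0.40 |
| 30% | 0.284 | 44% | 0.45 |
| 40% | 0.266 | 49% | 0.47 |

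By symmetry the power is the same for the inverse ratio, 1/0.6 = 1.67.

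**The case against.** The best defence is that the omission is deliberate. MCS can start after randomization and may be influenced by treatment, so a naive comparison within MCS groups would be biased. The footnote says so, and the stated purpose of the model is adjustment. On that view the SAP has withdrawn the subgroup contrast for a sound reason, and only a labelling inconsistency is left.

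The bias argument stands, and it limits the remedy: a Trt×MCS(t) term conditions on something treatment may affect, so it describes an association and not a randomized subgroup effect. It does not rescue the text as written. MCS is still a planned subgroup, and the footnote presents the Cox model as the substitute for its analysis, not as a reason to drop it.

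Four stronger readings are tempting but not supported:
- *No view of outcome by MCS is ever produced.* The SAP does plan MCS-stratified Kaplan-Meier curves. What is missing is a formal estimate or test of the treatment effect by MCS.
- *The forest-plot restriction is a fault.* Limiting forest plots to pre-randomization subgroups is good practice.
- *The repair certainly needs no new data.* Neither *Randomization* nor *Description of patients' characteristics* lists MCS at randomization, and *Additional analyses* computes event times from dates. Dates alone cannot separate MCS begun before randomization from MCS begun later the same day.
- *The primary result is affected*, because the SAP speaks of bringing these covariates into the outcome models. The primary clinical tests are a chi-square test and a one-sided Z-test, and *Additional analyses* excludes planned multivariate adjustment from the initial primary analysis.

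**Conclusion.** The concern holds in this form: the SAP lists MCS as a subgroup and assigns it a model that forces a common treatment HR. The model can adjust for support, but cannot estimate or test whether the cangrelor effect differs by MCS. It also leaves IMPELLA unmodelled. This follows from the printed equation and needs no simulation.

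The simulated HRs show what can be hidden, under assumed parameters; they do not predict this trial. The power range rests on the planned event rates and on an assumed 10% to 40% of events on MCS. At about 236 events, an interaction would be reliably detected only if it were very large, which calls for estimates with confidence intervals rather than reliance on a test.

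The matter is confined to one subgroup analysis and leaves the primary analysis alone. It should be corrected because a written rule cannot do the job given to it, and the repair is small.

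**What to change.** Amend *Subgroup analysis* and *Time-Dependent Covariate Analysis*:

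1. **MCS at randomization.** Where recorded start times allow, define the subgroup as MCS already running at randomization (yes/no). Analyse it alongside the other pre-randomization subgroups with an explicit treatment-by-MCS interaction, and show it on the forest plot. The interaction has to be written out, because the SAP names none for any subgroup. Remove the footnote wording that substitutes the Cox model for this analysis.
2. **Time-dependent MCS.** If the Cox model is kept, use one MCS(t) variable covering all the devices the SAP names, add Treatment × MCS(t), and report the treatment HR with and without MCS, with confidence intervals. Label it exploratory and non-causal, because later MCS may be affected by treatment.
3. **Fallback.** If MCS status at randomization cannot be determined and no effect by MCS is wanted, take MCS off the subgroup list and describe the model as an adjustment only.

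**Cost.** For options 2 and 3, SAP wording and at most a redefined MCS variable and one model term; the time-dependent model already needs MCS start times. Option 1 first needs a check that the case report form or source records place MCS start before or after randomization, which the SAP does not show. The price of options 1 and 2 is low power, which should be stated in the SAP.

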The DAPT-SHOCK AMI is a prospective, international, multicenter, randomized, double-blind controlled trial that compares the effects of parenteral cangrelor to the recommended treatment of crushed ticagrelor on i) periprocedural adenosine diphosphate (ADP) activated platelet aggregation and ii) the occurrence of major cardiovascular events in patients with acute myocardial infarction (AMI), initially in cardiogenic shock (CS).

Despite all the advances in the treatment of CS complicating AMI, early reperfusion remains the only therapy that reduces the high risk of death. The most effective restoration of coronary blood flow at the microcirculation level is ensured by mechanical reperfusion (percutaneous coronary intervention) and adjuvant antithrombotic treatment. Inhibitors of ADP-induced platelet activation, i.e., P2Y₁₂ inhibitors, are essential to combined antiplatelet therapy. Oral P2Y₁₂ inhibitors (e.g., ticagrelor) require hours to take full efficacy, and their effectiveness is furthermore impacted by splanchnic hypoperfusion in shock patients. Cangrelor, the only available parenteral P2Y₁₂ inhibitor with the immediate onset of action, is an ideal drug to bridge the time gap.

The hypothesis of the study is that intravenous cangrelor will be (a) more effective in terms of the rate of onset and the proportion of patients achieving effective periprocedural inhibition of ADP-induced platelet aggregation, and (b) at least as effective (the calculation of sample size for both superiority and non-inferiority) in reducing major cardiovascular events compared to the recently recommended treatment with crushed oral ticagrelor.

The timeline of the project is given in Figure 1.

Figure 1 Timeline of the project

Inclusion criteria

1. Men and women over 18 years of age.
2. Acute myocardial infarction, as defined by the universal definition of the ESC, ACC, and AHA indicated for emergent percutaneous coronary intervention (primary PCI strategy).
3. Cardiogenic shock at admission resulting from acute myocardial infarction and the presence of ≥ 2 criteria below:
 - Systolic blood pressure (sBP) < 90 mmHg,
 - The need for treatment with vasopressors and/or inotropes,
 - Presence of signs indicating organ hypoperfusion – cyanosis, cold peripheral parts, impaired consciousness, congestive heart failure.
4. Signed informed consent.

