5. Women of childbearing potential should be protected from pregnancy throughout the study (relevant for long-term use of ticagrelor). Suitable methods of contraception, in this case, include hormonal contraceptives, barrier methods, or complete withdrawal – as long as it is consistent with the patient's lifestyle.

Exclusion criteria

1. Contraindications to antiplatelet therapy with ticagrelor/cangrelor:
 - Recent (< 6 months) major bleeding,
 - Recent (< 1 month) major surgery/injury,
 - History of intracranial hemorrhage,
 - History of Stroke/TIA,
 - Known ticagrelor/cangrelor intolerance,
 - Severe hepatic impairment,
 - Co-administration of potent CYP3A4 inhibitors (e.g., ketoconazole, clarithromycin, nefazodone, ritonavir, and atazanavir).

2. Administration of a loading dose of oral P2Y₁₂ inhibitor before admission (clopidogrel ≥ 300 mg, ticagrelor 180 mg, prasugrel 60 mg).
3. Need for concomitant chronic anticoagulant treatment due to atrial fibrillation, artificial valve, thromboembolic disease, etc.

Study endpoints

Primary endpoint – laboratory

- Comparison of the effect of parenteral cangrelor with the recommended crushed ticagrelor treatment on periprocedural ADP-activated platelet aggregation; the periprocedural rate of onset and the proportion of patients who achieve effective* P2Y₁₂ platelet receptor inhibition defined by a Platelet Reactivity Index (PRI) value at the end of percutaneous coronary intervention.

**Platelet Reactivity Index (PRI) less than 50% as measured by the vasodilator-stimulated phosphoprotein (VASP) phosphorylation flow cytometric assay*

Primary endpoint – clinical

- Comparison of the effect of parenteral cangrelor with the recommended crushed ticagrelor treatment on the incidence of major cardiovascular events 30 days after enrollment in the study. The primary clinical endpoint is a composite of all-cause death, myocardial infarction, or stroke* within 30 days, expressed as a proportion of patients with any of these events. The primary clinical endpoint is non-inferiority, and if this is met, then superiority will be tested.

**Ischemic stroke (intracranial hemorrhage assessed as a BARC 3c bleeding)*

Secondary endpoints

Key secondary efficacy endpoint

- Death, myocardial infarction, urgent revascularization of the infarct-related artery, stent thrombosis, or ischemic stroke within 30 days and one year after study enrollment expressed as a proportion of patients with any of these events.

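### The per-protocol set is defined by full dosing alone, so its agreement with the MITT result says nothing about patients who broke the entry criteria

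*SAP*

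**What the plan says.** The *Analysis population* section of the SAP defines three sets. ITT is everyone randomized. For the primary set, "The MITT population includes all randomized patients in the trial who received a dose of the study drug". For the third set, "the PP population consists of all randomized patients who received the full dose of the study drug as per protocol". On their use it says that "analyses based on ITT and PP populations will be considered secondary and confirmatory", and on arm assignment that "Treatment classification in all scenarios will be based on the randomized treatment".

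The entry criteria are listed earlier. *Inclusion criteria*, item 3, requires "Cardiogenic shock at admission resulting from acute myocardial infarction and the presence of ≥ 2 criteria below". *Exclusion criteria* rule out, among others, "Administration of a loading dose of oral P2Y₁₂ inhibitor before admission" (item 2) and "Need for concomitant chronic anticoagulant treatment due to atrial fibrillation, artificial valve, thromboembolic disease, etc" (item 3).

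Nothing in the SAP links these criteria to the PP set. The one deviation it names, a visit outside its window (*Schedule of study visits*), is not linked to the PP set either. There is no list of major deviations and no rule for a blinded review of set membership.

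**The concern.** In the definition, the reference to the protocol qualifies the dose received, not eligibility. PP therefore differs from MITT in one respect only: it drops patients whose dosing was incomplete. A patient entered in breach of the criteria but fully dosed stays in every set.

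This matters because of the order of testing. Under *Primary endpoint – clinical*, "The primary clinical endpoint is non-inferiority, and if this is met, then superiority will be tested". Beside a non-inferiority test, one reason to run a PP analysis is to see whether the main result has been pulled towards no difference by patients in whom the treatments could hardly differ. An excluded P2Y₁₂ load is the clearest example. As written, the PP analysis cannot address that question, and a reader who sees PP and MITT agree may take more reassurance than the comparison can give.

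**Working it through.** **Step 1: who is in which set.** Take a randomized, fully dosed patient who failed one entry criterion.

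| Set | Condition in the SAP | Patient included? |
|---|---|---|
| ITT | randomized | yes |
| MITT | randomized, received a dose | yes |
| PP | randomized, full dose | yes |

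The point rests on this step. The rest shows how large the effect could be.

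**Step 2: reproduce the SAP's figures.** Inputs from the power-analysis sections: power 0.8, significance level 0.05, control rate 50%.

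- Superiority, 50% v 38%, two-sided, mean rate 0.44: n per arm = [1.960·√(2·0.44·0.56) + 0.842·√(0.50·0.50 + 0.38·0.62)]² / 0.12² = 267.4, so 268 per arm and 536 in total, as stated.
- Non-inferiority, 50% v 40%, margin 1 point, one-sided 0.05, mean rate 0.45: n per arm = [1.645·√(2·0.45·0.55) + 0.842·√(0.50·0.50 + 0.40·0.60)]² / 0.11² = 252.1, so 253 per arm and 506 in total, as stated.

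**Step 3: dilution.** Let v be the share of ineligible patients. The SAP does not give v, so 5%, 10% and 15% are assumed. Assume also that these patients have a 50% event rate in both arms. As a simplification, all 536 patients are treated as fully dosed.

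Diluted difference: d = 12·(1 − v) points. With p₂ = 0.50 − d (d as a proportion) and p̄ the mean of 0.50 and p₂:

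power = Φ{[d − 1.960·√(2p̄(1−p̄)/n)] / √[(0.25 + p₂(1−p₂))/n]}

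Here n = 268 per arm for the diluted set. For eligible patients only, n = 268(1 − v) and the rates are 50% v 38%.

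Example, v = 10%: d = 0.108, p₂ = 0.392, p̄ = 0.446. Power = Φ[(0.108 − 0.0842)/0.0427] = 0.712.

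| v | Difference kept (points) | Power, ineligible kept | Power, eligible only (12 points) |
|---|---|---|---|
| 0% | 12.0 | 0.801 | 0.801 |
| 5% | 11.4 | 0.758 | 0.780 |
| 10% | 10.8 | 0.712 | 0.758 |
| 15% | 10.2 | 0.661 | 0.734 |

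**Step 4: false non-inferiority.** Suppose cangrelor is truly worse by exactly the 1-point margin in eligible patients and no different in the rest. The true difference in the set is then 1·(1 − v) points. With n = 268 per arm, a one-sided test at 0.05 and a 50% control rate, P(non-inferiority declared) = Φ[(0.01 − 0.01(1 − v))/SE − 1.645]. This is 5.00% at v = 0, 5.12% at 5%, 5.24% at 10% and 5.50% at 20%.

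**Step 5: how visible the shift would be.** Removing the ineligible patients moves the estimate by 12·v points. The standard error of that shift is v·√(Var_eligible + Var_ineligible), where Var_eligible = (0.25 + 0.38·0.62)/[268(1 − v)] and Var_ineligible = (0.25 + 0.25)/(268v).

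| v | Expected shift (points) | Standard error (points) |
|---|---|---|
| 5% | 0.6 | 1.0 |
| 10% | 1.2 | 1.4 |
| 15% | 1.8 | 1.8 |

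**The case against.** The case for leaving the definition alone has several sound parts.

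- **Nothing hangs on PP.** MITT is primary, no decision rule uses the PP result, and a definition by treatment received is clear and reproducible. This stands, and it limits the weight of the point. It does not answer why an analysis called confirmatory should keep patients the entry criteria exclude.
- **The non-inferiority risk is tiny.** With a 1-point margin, Step 4 moves the error rate by a quarter of a percentage point at v = 10%. A reader might infer that the non-inferiority conclusion is in danger; the SAP's own figures do not support that.
- **The shift would be hard to see.** By Step 5 it is at most about one standard error for v up to 15%. The amended PP set would be a cleaner description of the eligible population, not a sharp test for dilution.
- **Zero contrast is near the worst case.** A patient needing anticoagulation still receives one or other P2Y₁₂ inhibitor. A patient not in shock may keep some contrast and would hardly share a 50% event rate. The Step 3 figures are therefore upper-end for a given v.
- **The planning figures do have a matching set.** A reader might infer that no set corresponds to them. The power-analysis section for the primary clinical endpoint bases the sample size on patients who receive the initial dose, which is MITT. Only the entry criteria lack a matching set.
- **Frequency is unknown.** It is tempting to infer from abbreviated or witnessed consent that late-found ineligibility is likely. Those are permitted procedures, and the SAP gives no rate.
- **Discovery can depend on survival.** Eligibility is fixed before randomization, but a prior load or anticoagulant need may never be documented in a patient who dies early. With a planned control event rate of 50%, exclusion based on history learned later would tend to remove survivors. This stands and shapes the remedy.

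**Conclusion.** The point holds in a limited form. The SAP states a complete PP rule that depends on dosing only, with no reference elsewhere for further conditions. Run as written, the PP analysis keeps fully dosed patients who broke the entry criteria, and its agreement with MITT carries no information about them.

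The size depends on two assumptions that the SAP cannot settle: the share of ineligible patients, and the absence of any treatment contrast among them. Under both, the loss for v between 5% and 15% is 0.6 to 1.8 points of the planned difference and about 4 to 14 percentage points of power. Restriction to eligible patients recovers about 2 to 7 of those percentage points.

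A reader might go further and take the primary result to be compromised. The documents do not support that: the MITT analysis and the sample size do not depend on how PP is defined. Any dilution would be present in MITT too, and redefining PP would not remove it there. The point is a worthwhile, inexpensive improvement to a secondary analysis.

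**What to change.** Add to the PP definition that, besides full dosing, patients must have met all inclusion and no exclusion criteria. State three conditions:

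1. Eligibility is judged only from information documented at or before randomization, not from history learned because the patient survived.
2. The judgement is made by reviewers blind to arm and outcome, before database lock.
3. Patients removed are listed by reason and by arm once the blind is broken.

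Keep MITT as the primary set.

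The cost is a short addition to the SAP and one blinded listing. Much of the material should exist: the SAP has the monitor compare the eCRF with source documents, and the planned patient characteristics include admission blood pressure, vasopressor and inotrope treatment, and chronic antiplatelet medication. Sample size and primary analysis do not change.

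There are two downsides: a slightly smaller PP set, and possibly incomplete detection of breaches in patients who die early. The second should be acknowledged when the PP result is reported.

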The study is double-blind. However, in the case of a clinically emergent situation in which knowledge of the treatment is essential, it is possible to "unblind" the administered medication during the first four hours after randomization (i.e., to obtain information on which of the drugs -

cangrelor or ticagrelor is being used to treat the patient in the first four hours). This situation is recorded using an online eCRF option. In the further course of the study, all patients are treated with ticagrelor.

Randomization of patients with impaired consciousness

Acute myocardial infarction complicated by CS is a life-threatening situation. The manifestation of circulatory failure is often accompanied by simultaneous disturbances of consciousness, the need for artificial lung ventilation, or mechanical circulatory support. If, for these reasons, obtaining informed consent before inclusion in the clinical trial is not possible, the consent of the patient's representative is required. If this representative is not appointed or available, the patient will be enrolled after an independent witness has signed the informed consent form, confirming through their signature that the trial subject has been enrolled according to the procedure outlined in the protocol approved by the ethics committee (date, name, and signature). The patient's consent to continue in the study will be obtained immediately after the patient's health status improves.

Validation of data collection

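### The per-protocol set requires the full dose with no exception for dosing cut short by death or another primary-endpoint event, so membership depends partly on the outcome

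*SAP*

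**What the plan says.** Three populations are defined under Analysis population in the SAP.

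- **MITT:** "The MITT population includes all randomized patients in the trial who received a dose of the study drug".
- **ITT:** everyone randomized.
- **PP:** "the PP population consists of all randomized patients who received the full dose of the study drug as per protocol".

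Their roles are fixed in the same section: "The MITT will serve as the primary analysis approach; analyses based on ITT and PP populations will be considered secondary and confirmatory".

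Under Study endpoints, "The primary clinical endpoint is a composite of all-cause death, myocardial infarction, or stroke* within 30 days". The order of testing is also given there: "The primary clinical endpoint is non-inferiority, and if this is met, then superiority will be tested". The Statistical analysis section specifies a one-sided Z-test with a margin of 1%.

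The SAP does not define the full dose or say how long dosing takes. The nearest indication is the Unblinding section, which speaks of finding out whether "cangrelor or ticagrelor is being used to treat the patient in the first four hours" and then states: "In the further course of the study, all patients are treated with ticagrelor". This implies a blinded study-drug period of about four hours.

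**The concern.** The PP rule is stated without exception. Read literally, a patient who starts study drug and dies before completing it counts as an event in MITT and ITT but disappears from PP. The reason for the exclusion is itself a primary-endpoint event, so PP membership is selected on the outcome. The same applies if a myocardial infarction or stroke stops dosing.

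This population is at high risk: the Safety analysis section puts mortality in cardiogenic shock above 50%, although that is not mortality in the first hours. If early deaths differ between the arms, whether by chance or through a real treatment effect, PP drops more events from one arm than from the other. It could then appear to support non-inferiority wrongly, or to contradict a sound primary result.

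The rule also sits badly with the SAP's own approach elsewhere. For mechanical circulatory support, the SAP uses time-dependent models to avoid survivor bias and limits forest plots to pre-randomization subgroups.

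**Working it through.** **Inputs from the SAP (Sample size calculation; Statistical analysis).** Control rate 50%; non-inferiority planned at 50% vs 40% with a margin of 1 point; superiority planned at 50% vs 38%; significance level 0.05; power 0.8; 1:1 allocation; 506 patients for non-inferiority and 536 for superiority, counted as patients who receive the initial dose.

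**Reproducing the stated sizes.**
- Non-inferiority, pooled variance, one-sided 0.05: n per arm = 2 × 0.45 × 0.55 × (1.645 + 0.842)² / (0.10 + 0.01)² ≈ 253, total 506, which matches. One-sided 0.025 would give 644, so 0.05 one-sided is the level behind the plan and is used below.
- Superiority, 50% vs 38%, two-sided 0.05: 268 per arm, total 536, which matches.

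**Assumption.** Let e be the share of an arm that starts study drug but is excluded from PP because death or another primary event stopped dosing. The SAP gives no figure for e; the range tried is 0 to 10%. Each excluded patient is an event, so an arm with true 30-day rate p shows in PP

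rate = (p − e) / (1 − e).

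The true 30-day rates are held fixed while e varies, so where e is unequal, later events are assumed to offset the early gap.

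**Test.** One-sided Z-test, unpooled variance, 268 per arm before exclusion. With D = cangrelor rate minus ticagrelor rate as seen in PP,

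P(declare non-inferior) = Φ[(0.01 − D)/SE − 1.645].

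**At the non-inferiority boundary (cangrelor 51%, ticagrelor 50%).** With no exclusion, SE = √(0.51 × 0.49/268 + 0.50 × 0.50/268) ≈ 0.043.

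| Excluded: cangrelor / ticagrelor | PP rates: cangrelor / ticagrelor | D (points) | Type I error |
|---|---|---|---|
| 0 / 0 | 51.0% / 50.0% | +1.0 | 0.050 |
| 2% / 2% | 50.0% / 49.0% | +1.02 | 0.050 |
| 5% / 5% | 48.4% / 47.4% | +1.05 | 0.049 |
| 10% / 10% | 45.6% / 44.4% | +1.11 | 0.048 |
| 2% / 0 | 50.0% / 50.0% | 0.0 | 0.079 |
| 5% / 0 | 48.4% / 50.0% | −1.6 | 0.146 |
| 0 / 5% | 51.0% / 47.4% | +3.6 | 0.012 |

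Example, 5% of cangrelor only: (0.51 − 0.05)/0.95 = 0.484; D = 0.484 − 0.500 = −0.016; 268 × 0.95 ≈ 255 patients remain in that arm; SE ≈ 0.0437; Φ[(0.01 + 0.016)/0.0437 − 1.645] ≈ 0.146. Excluding 2% of one arm means about 0.02 × 268 ≈ 5 patients.

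**At the planned alternative (50% vs 40%).** The chance of declaring non-inferiority is 0.823 with no exclusion, 0.950 with 5% of cangrelor only excluded, and 0.613 with 5% of ticagrelor only excluded. The distortion can go either way.

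**The case against.** **The primary conclusion does not rest on PP.** MITT is primary and includes anyone who received a dose; ITT includes everyone randomized. Both count the early deaths. The SAP never makes non-inferiority conditional on agreement in PP, nor lets PP override MITT; that PP would be read as support for non-inferiority follows only from its confirmatory label and the primary hypothesis. This stands and limits the point to one secondary analysis.

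**The definition refers to the protocol.** The protocol is not shown and might say how dosing stopped by death is classed. This stands in part: it could soften the effect. But the SAP chose to state the membership rule itself, so this is a rule to be corrected rather than detail left elsewhere.

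**The size is assumed.** The SAP gives no early-death rate, a material effect needs an imbalance, and only deaths during the dosing period count, not all 30-day deaths. This stands; the table is a range, not a forecast.

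**Two stronger readings are not supported.** A reader might infer that cangrelor must lose more patients because an infusion takes longer to complete than a crushed oral load. The SAP gives no infusion duration or dosing schedule, the trial is double-blind, and the Unblinding section treats either drug as in use over the four hours. A reader might also reason that a shift larger than the 1-point margin settles the test. With an SE of about 4.3 points, passing requires an observed difference near 1 − 1.645 × 4.3 ≈ −6 points, so a 1-point shift is only about a quarter of an SE. The effect on error rates, not comparison with the margin, is the right measure.

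**Conclusion.** The point holds as a defect in the PP definition. Completion of dosing is required without exception, death can prevent completion, and death is a primary-endpoint event; the selection on outcome follows from the wording alone. Its direction and size cannot be determined from the SAP. Balanced early exclusions are harmless to the comparison, while one-arm exclusions of up to 5% put type I error of the PP test anywhere from about 0.01 to 0.15 against a nominal 0.05. These figures rest on assumed exclusion shares, fixed 30-day rates, 268 per arm and one-sided 0.05. The consequence is a PP result that may mislead beside the primary analysis. It is not a threat to the MITT or ITT result, and the documents give no ground for saying which arm would be favoured.

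**What to change.** Add one clause to the PP definition under Analysis population: patients who started the allocated study drug and whose dosing was cut short by death or another primary-endpoint event remain in the PP set, with the event counted. State that PP membership is decided blind to treatment before database lock, and report PP exclusions by arm and reason alongside the CONSORT diagram.

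The cost is a short SAP amendment, with no new data and no change to sample size or treatment. The small downside is that the PP set will include some patients who did not receive the full dose. The change should precede unblinding, since choosing the rule afterwards would be data-dependent.
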